#### 5.3.2 Sensitivity analysis

#### 5.3.2.1 Per Protocol Population

For the PP analysis, participants who have engaged with at least one of the two group session of the programme will be included. The PP will adhere to the same steps as the primary analysis.

#### 5.3.2.2 Intention-to-treat Population

To allow for full analysis set, missing data will be imputed using a multiple imputation procedure which substitutes predicted values from a regression equation. The imputation will be carried out by the MI command in Stata 15. MI replaces missing values with multiple sets of simulated values to complete the data, performs standard analysis on each completed dataset, and adjusts the obtained parameter estimates for missing-data uncertainty using Rubin's rules to combine estimates.

The following procedure will be followed:

• The MI will be set as wide

• The MI will register imputation of the overall volume of physical activity at 12 months and at baseline

• A regression method will be used , where the registered variables will be individually adjusted for the randomisation and stratification factors (age and ethnicity), with 100 imputations to avoid biased estimates, rseed (2259) and the force options

• MI estimate will provide the final results using the same regression model as the primary analysis and covariate adjustments.

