#### 3.3.2 Intention-to-treat Population /Full analysis data

A sensitivity analysis using multiple imputation will be used to impute missing data, to assess the robustness of the conclusions to missing data. This will be a full intention to treat analysis. More detail is in section 5.3.2.2.

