#### (i) Ambulatory activity:

Participants will be asked to wear an accelerometer for eight days to record total volume of physical activity, which includes light, moderate, vigorous and moderate to vigorous physical activities (MVPA) and to complete an activity log to provide wear time information. To be included in an analysis a participant needs to provide at least one valid day of accelerometer data.

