# 5.3 Analysis methods

#### 5.3.1 Analysis of primary outcome

The primary outcome is change in overall volume of physical activity (average acceleration, ENMO) from baseline to 12 months. For the primary outcome treatment arm will be compared using linear regression modelling with a binary indicator for randomisation group as the explanatory variable, terms for stratification factors (age and ethnicity) as confounders, and adjustment for the change in accelerometer wear time from baseline and overall volume of physical activity at baseline.

The primary analysis at 12 months will be based on complete data.

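### The multiple-imputation analysis leaves wear time unimputed but adjusts for it, so about 203 to 232 of 290 participants are analysed and it is not full intention to treat

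*SAP*

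**What the plan says.** SAP 3.3.2 introduces multiple imputation as the sensitivity analysis for missing data and states its status: "This will be a full intention to treat analysis".

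SAP 5.3.2.2 then sets out the procedure.

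- Variables to impute: "The MI will register imputation of the overall volume of physical activity at 12 months and at baseline".
- Imputation model: "the registered variables will be individually adjusted for the randomisation and stratification factors (age and ethnicity), with 100 imputations".
- Analysis of the completed data: "MI estimate will provide the final results using the same regression model as the primary analysis and covariate adjustments".

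The primary model is in SAP 5.3.1. Besides arm and the two stratification factors it includes "adjustment for the change in accelerometer wear time from baseline and overall volume of physical activity at baseline".

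Wear time is described in SAP 5.2 (i). Participants wear the monitor for eight days and are asked "to complete an activity log to provide wear time information". The rule for entering an analysis is that "a participant needs to provide at least one valid day of accelerometer data".

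**The concern.** Change in wear time needs a wear time at 12 months. A participant who does not return at 12 months has neither an activity value nor a wear time. The procedure fills in the first and leaves the second empty. Linear regression omits any row with a missing covariate, so the imputed outcome is created and then never used. More imputations do not help, because the same rows fall out of every completed dataset.

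This matters because SAP 3.2 relies on the sensitivity analyses in 5.3.2 to show whether the findings are robust to missing data, and only multiple imputation could do so:

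- The primary analysis is complete case (3.3.1, 5.3.1).
- The per-protocol set also requires complete outcome data (3.3.3).
- The valid-day models restrict the sample further (5.3.2.3).

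If the imputation analysis runs on the complete cases, or on little more, its agreement with the primary result is wholly or largely built in and says little about missing data.

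**Working it through.** **1. The SAP's sample size (2.3).** Inputs: difference 2.1 mg, SD 5.3 mg, power 80%, significance level 5%, two-sided (3.1), allocation 1:1 (2.1).

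- Normal approximation: n per arm = 2 × (1.960 + 0.842)² × 5.3² / 2.1² = 2 × 7.849 × 28.09 / 4.41 = 99.99, so 100 per arm, 200 in total.
- Solving with the t distribution gives 100.96, so 101 per arm, 202 in total. This matches the SAP.
- Inflation: 202 / (1 − 0.30) = 288.6, so 289, or 290 with equal arms. This also matches, and it shows that the 20% and 10% are added. SAP 3.3.1 likewise speaks of 30%.

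**2. Expected missing outcomes at 12 months.**

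- Lost to follow-up: 290 × 0.20 = 58.
- Monitor non-compliance: 290 × 0.10 = 29.
- Without a 12-month outcome: 58 + 29 = 87.
- Complete cases: 290 − 87 = 203.

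**3. Rows that survive the refitted model.** A row is kept only if change in wear time is present.

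- If none of the 87 has a 12-month wear time: 203 rows, the same people as complete case.
- If all 29 non-compliers have a recorded wear time despite having no valid day: 290 − 58 = 232 rows.
- The 58 lost to follow-up are absent in both cases.

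These counts take baseline accelerometry as complete. Anyone whose baseline activity is imputed because the baseline recording is missing has no baseline wear time either, and is lost in the same way.

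**4. Illustration by simulation.** One dataset of 290 was generated with 58 lost and 29 non-compliant. Twelve-month activity was imputed 100 times from arm, age and ethnicity. The 5.3.1 model was then fitted to each completed dataset and the results pooled by Rubin's rules, total variance = W + (1 + 1/100) × B, where W is the mean within-imputation and B the between-imputation variance.

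| Wear-time change available for | Rows used | Estimate (mg) | SE | B |
|---|---|---|---|---|
| Complete-case fit, for reference | 203 | 2.7055 | 0.6141 | – |
| Those with an outcome only | 203 | 2.7055 | 0.6141 | 0 |
| Those with an outcome plus the 29 non-compliers | 232 | 2.9971 | 0.6642 | 0.081 |
| Everyone | 290 | 3.0716 | 0.6962 | 0.156 |

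In the second row all 100 fits are the same fit, so B is zero and the pooled result is the complete-case result. The activity and wear-time values were invented for the purpose, and the last row uses the simulated wear times themselves, not imputed ones. The estimates and SEs therefore show the mechanism only. The row counts follow from the SAP's figures.

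**The case against.** The strongest points on the other side are these.

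**Not everyone with an imputed outcome need drop out.** A reader might infer that all 87 do, so that the analysis always reduces to complete case. The SAP does not support that as a certainty. SAP 5.2 (i) takes wear-time information from an activity log and ties inclusion to a valid day of accelerometer data. Someone with a log or a short recording could have a wear time but no valid outcome. This stands, and it is why the result is a range.

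**The SAP intends all missing data to be imputed.** The opening of 5.3.2.2 says so in general terms. But the steps that follow name the registered variables, and wear time is not one of them. An analyst who follows the steps loses the rows. No section assigns a wear time, zero or otherwise, to people without a recording.

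**The force option might be blamed.** 5.3.2.2 specifies "with 100 imputations to avoid biased estimates, rseed (2259) and the force options". That option belongs to the imputation step. The predictors there are arm and the randomisation strata, and wear time is absent. The rows are lost later, in the analysis model, so removing the option would not expose this defect.

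**It is only a sensitivity analysis.** This is true. The primary estimate, its confidence interval and the sample size do not change. A reader might also infer that the agreement will be reported as proof of robustness. The SAP does not say that, and an alert analyst could notice the row count. But the SAP does not ask for the number analysed, and there is no second analysis to fall back on.

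**Conclusion.** The point holds as a contradiction within the SAP. Following 5.3.2.2 with the model in 5.3.1 cannot produce the analysis described in 3.3.2. At the SAP's own attrition about 203 to 232 of 290 participants are analysed, so between 58 and 87 are left out. At the lower end the result is the complete-case result under another name. At the upper end it differs from complete case only through the non-compliers, and everyone lost to follow-up is still missing.

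The exclusion of the 58 rests on their having no 12-month wear time, which follows from their being lost. Where the figure falls between 203 and 232 depends on how many non-compliers have a usable wear time, which the SAP does not say; probably most do not. The range assumes that attrition is as planned and that baseline recordings are complete.

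This is a stated rule that gives the wrong result, not a missing detail. It should be corrected before the analysis is run, although the primary result does not depend on it.

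**What to change.** Amend SAP 5.3.2.2 in one of two ways.

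1. **Preferred, because it keeps the primary model.** Register wear time at baseline and at 12 months as well as activity at both times. Impute the four variables jointly by chained equations, with arm and the stratification factors as predictors. Derive the changes from the imputed values and refit the 5.3.1 model.
2. **Alternative.** Omit change in wear time from the model fitted to the imputed data. Include baseline activity as a predictor when imputing 12-month activity, since the analysis model contains it and the present imputation model does not. Also report a complete-case fit of the same reduced model. Otherwise the two results would differ in covariates as well as in the handling of missing data.

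In both cases require the number analysed to be reported. It should equal all randomised participants other than those whom SAP 3.2 excludes for not attending the baseline assessment.

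The cost is a few lines of SAP wording and Stata code. No new data are needed.

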#### 5.3.2.3 Effects on the number of valid days

Three separate models will be run; including participants who have worn accelerometer for the following:

- At least 2 valid days
- At least 3 valid days
- At least 4 valid days

#### 5.3.3 Analysis of secondary outcomes

The analyses of the secondary outcomes will be conducted in a similar manner as the main analysis using the appropriate model type, logistic regression for binary outcomes, linear for continuous and ordinal for ordinal outcome.

The assumptions of each analysis will be assessed and alternate parameterisations will be considered where appropriate.

#### 5.3.4 Subgroup analyses for primary outcome

We will conduct the following subgroup analyses to assess if the intervention effect is statistically different between these groups.

- Age (<> median)
- Number of episodes of GDM ( 1 and  $\geq$ 2)
- BMI categories (Normal, overweight, obese) calculated according to ethnicity threshold.
- BMI pre-pregnancy as above but subject to obtaining the data
- Ethnicity (White, South Asian, other)
- Parity (1 and  $\geq$ 2)
- Sessions attended attended at least one session by used App and did not use App in categories:
  - (1) did not register to use App,
  - (2) registered but used App <10 times over 12 months,
  - (3) registered and used the App fairly frequently

The main analysis for each subgroup will involve using the same analytic principles as the primary analysis, but stratifying by the subgroup to estimate the mean difference in the overall volume of physical activity when compared to the control group. Further subgroup analyses will investigate the interaction effects between the treatment and subgroup, this will include an additional interaction term to the model; 'subgroup × treatment'. Subgroup results will be graphically presented as forest plots, with the estimated difference of overall volume of physical activity between treatment groups with 95% confidence interval for the interaction.

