# 2 Methods

# 2.1 Trial design

The trial is a parallel group randomised controlled trial, in which participants are randomised to two groups (1:1). It will compare a structured education programme plus additional follow on support (a wrist worn activity monitor and interactive web based intervention) with usual care plus an information leaflet. The RCT will be conducted in two centres; University Hospitals of Leicester NHS Trust and George Eliot Hospital NHS Trust. Participants will be followed up for 12 months.

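### The sessions/App-use subgroup in SAP 5.3.4 exists only in the intervention arm, so its interaction with treatment cannot be estimated and its comparison with controls is not randomised

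*SAP*

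**What the plan says.** Section 5.3.4 of the SAP sets out seven subgroup analyses of the primary outcome, intended "to assess if the intervention effect is statistically different between these groups". Six rest on characteristics that women in both arms have: age, number of GDM episodes, BMI, pre-pregnancy BMI, ethnicity and parity. The seventh concerns engagement with the programme: "attended at least one session by used App and did not use App in categories". Its three levels are "did not register to use App", "registered but used App <10 times over 12 months" and "registered and used the App fairly frequently".

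One rule then covers all seven items. The main analysis is described as "stratifying by the subgroup to estimate the mean difference in the overall volume of physical activity when compared to the control group". After that, "Further subgroup analyses will investigate the interaction effects between the treatment and subgroup", by adding a subgroup-by-treatment product term to the model. Results go on a forest plot with a 95% confidence interval for the interaction. The engagement item is not exempted, and it is not labelled exploratory or non-randomised.

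Section 2.1 gives the education programme, the activity monitor and the web-based support to the intervention arm, and compares this "with usual care plus an information leaflet". Section 3.3.3 applies an attendance criterion to the intervention arm only; controls enter the per-protocol set on complete outcome data alone.

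**The concern.** A subgroup analysis asks whether the randomised difference varies between kinds of participant. For that, each kind must be identifiable in both arms and must not itself result from allocation. App use counted over 12 months meets neither condition. It accrues during follow-up, and controls are given nothing to attend or register for.

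Two things are at stake. First, part of a pre-specified analysis cannot be carried out as written, so the analyst would have to choose a substitute once the data are in hand. Second, the part that can be carried out may show a gradient across App-use categories that reflects who chooses to use the App. On a forest plot beside true subgroups, that gradient would read as effect modification.

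**Working it through.** **1. The plan's own figures.** Section 2.3 gives a target difference of 2.1 mg, SD 5.3 mg, 80% power and 5% significance; section 3.1 makes p-values two-sided. A two-sample t-test calculation gives 100.96 per arm, so 101 per arm and 202 in total, as stated. Allowing for 30% loss, 202 / 0.70 = 288.6, so 289, or 290 for equal arms, as stated. These figures are not in dispute; 2.1 and 5.3 mg are used below as scale.

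**2. Can the interaction be estimated?** Let T = 1 for intervention and 0 for control, and let D2 and D3 indicate App categories 2 and 3. The prescribed model contains 1, T, D2, D3, T×D2 and T×D3. No control is in category 2 or 3, so D2 = D3 = 0 whenever T = 0. Hence T×D2 = D2 and T×D3 = D3 for every participant: the product columns copy the category columns. A numerical check of the design matrix with 101 per arm gave:

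| Coding of controls | Columns | Rank |
|---|---|---|
| Categories present in both arms (true subgroup, for comparison) | 6 | 6 |
| Controls coded as not registered | 6 | 4 |
| Controls given a level of their own | 8 | 4 |
| Controls missing and dropped | 6 | 3 |

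Under none of the three codings available for this item is the interaction identified. In the last, the treatment effect is lost as well. This step needs no assumption about the data beyond controls having no App use.

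**3. What does the stratified step estimate?** Read as each App category against all controls, it can be computed. It equals any effect in that category plus the difference between those users and an average control that would exist without the programme. The documents give no figure for that second part, so an assumption is needed.

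Assume that frequent users would be 0.3 SD more active at 12 months without the programme: 0.3 × 5.3 = 1.59 mg. Suppose the programme has no effect. Section 5.3.1 adjusts for baseline activity, and section 5.3.4 carries the same principles over, so the result depends on how much of the gap is visible at baseline.

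- Gap unrelated to baseline activity: all of it remains, 1.59 mg; 1.59 / 2.1 = 76% of the target.
- Gap fully present at baseline and stable, with slope b of 12-month on baseline activity: the remainder is (1 − b) × 1.59.
  - b = 0.5 (assumed): 0.5 × 1.59 = 0.80 mg; 0.80 / 2.1 = 38%.
  - b = 0.8 (assumed): 0.2 × 1.59 = 0.32 mg; 0.32 / 2.1 = 15%.

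**4. Shape of the bias.** A simulation with no treatment effect split the intervention arm into thirds by a latent motivation with assumed correlation r with the outcome. For r = 0.1, 0.2, 0.3 and 0.5, the top third differed from controls by about +0.6, +1.1, +1.7 and +2.9 mg, and the bottom third by about −0.6, −1.1, −1.7 and −2.8 mg. It had no baseline adjustment, so these sizes do not describe the planned model. They show that selection alone produces a gradient across the categories.

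**The case against.** The strongest reply is that this is one of seven subgroup analyses, and that the interaction failure would be plain to the analyst because the software would omit the collinear terms. That is fair, and it bears on how serious the point is. It does not remove the point: no passage exempts or relabels the item.

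A reader might go further than the SAP supports in four ways.

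- *That the whole item fails to run because no App category contains a control.* The stratified step is worded as a comparison with the control group, which allows each category to be set against all controls. Only the interaction step fails; the fault in the stratified step is selection.
- *That the likely bias is 76% of the target.* That is one assumed gap, passed through untouched by the planned baseline adjustment. If the gap is stable and present at baseline, much of it is removed. Adjustment cannot, however, be relied on to remove differences in readiness to change.
- *That the trial's main result is threatened.* The primary model in 5.3.1 and the sample size in 2.3 do not use App use or attendance.
- *That the SAP states outright that controls cannot use the App.* It does not. This is inferred from what section 2.1 provides to each arm and from the one-sided attendance rule in 3.3.3. The inference is strong.

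**Conclusion.** The item is wrong as written and should be corrected, though it is not critical to the trial's main conclusion. The interaction and its confidence interval do not exist for the sessions/App-use item; this is algebra, given that controls have no App use. The comparison of each App category with all controls can be computed but is not a randomised comparison, so it cannot answer the question that 5.3.4 poses.

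The size of the selection bias is unknown. With an assumed 0.3 SD gap it ranges from about 0.3 mg to 1.6 mg against a 2.1 mg target, depending on how far the gap is already present at baseline and on an assumed baseline slope of 0.5 to 0.8. A different gap would scale these figures in proportion.

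**What to change.** Remove the sessions/App-use item from the subgroup list, the interaction test and the subgroup forest plot in 5.3.4. Report attendance and App use descriptively within the intervention arm. If App-use categories are still compared with controls, present this separately and label it exploratory and non-randomised, not effect modification. If the three categories are kept for description, give the third a numerical lower bound; the second suggests 10 uses, which the sponsor should confirm.

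A complier-average analysis with App use at that threshold as the definition of compliance may look like a natural replacement, but it should not be added. It would need the programme to have no effect in women who attended the education sessions but used the App less. That is implausible when section 1.2 makes structured education the intervention under test.

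The cost is a short SAP edit and the loss of one nominal subgroup test. No new data are needed.

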# 2.3 Sample size

The primary outcome is based on increasing total physical activity as quantified by the Euclidean norm minus one (ENMO) method measured in milligravity units (mg). This is the

main measure of activity derived from the GENEActiv monitor. In order to detect a minimum clinically significant difference of 2.1 mg, which is equivalent to an overall increase in physical activity volume of approximately 30 minutes of brisk walking at 4km/h, assuming a standard deviation of 5.3 mg , a power of 80% and significance level of 5%, the sample size requires 202 participants. To allow for 20% loss to follow-up and 10% non-compliance of the GENEActiv monitor, we will therefore need to recruit 290 participants (145 in each arm).

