# 3 Statistical principles

### 3.1 Confidence intervals and p-values

The estimates of effect will be reported with 95% confidence intervals, for both primary and secondary outcomes. All p-values shown will be two sided.

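### The SAP's subgroup section ranks within-stratum models above the interaction test its aim calls for, and its forest plot pairs each treatment difference with the interval of a different parameter

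*SAP*

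**What the plan says.** All of the relevant text on method is in SAP section 5.3.4.

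- **Aim.** The subgroup analyses are run "to assess if the intervention effect is statistically different between these groups".
- **Main method.** "The main analysis for each subgroup will involve using the same analytic principles as the primary analysis, but stratifying by the subgroup", in order to estimate the mean difference from control within each stratum.
- **Further method.** A treatment-by-subgroup term is then added to the model. No interaction p-value or joint test is named as the basis for a conclusion.
- **Display.** Forest plots are to show results "with the estimated difference of overall volume of physical activity between treatment groups with 95% confidence interval for the interaction".

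Seven subgroup factors are listed. Current BMI, pre-pregnancy BMI (if the data can be obtained) and ethnicity have three levels each. The last factor is defined by sessions attended and use of the App. The section neither labels the subgroups exploratory nor mentions multiplicity.

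**The concern.** Whether an effect differs between subgroups is a question about a difference of differences. Only the interaction estimates that quantity. A within-stratum model answers another question: how large the effect is in that stratum. Ranking the stratum models first reverses the order that the aim needs. It invites the common misreading in which an effect significant in one stratum and not in another is taken as evidence of effect modification.

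The plot instruction is a separate fault. The point is a treatment difference and the interval belongs to the interaction. The two have different centres and different standard errors, so the interval would not express the uncertainty of the point it is drawn around. For a three-level factor the instruction cannot be followed at all, because there are two interaction coefficients and no single interaction interval.

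At stake is the interpretation of the subgroup results. The primary estimate is not affected.

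**Working it through.** **Inputs from the SAP.** Section 2.3 gives a "minimum clinically significant difference of 2.1 mg", "assuming a standard deviation of 5.3 mg", 80% power, 5% significance, 202 evaluable and 290 recruited. Section 2.1 gives 1:1 allocation. Section 3.1 says "All p-values shown will be two sided".

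**Assumed, because the SAP does not give it.** Subgroup sizes: two strata, split 50/50, 70/30 or 80/20, with the same split in each arm of 101.

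**Step 1: the plan's own figure.** A two-sample t-test with a standardised effect of 2.1/5.3 needs 100.96 per arm, rounded up to 101, so 202 in total. This matches exactly (the normal approximation gives 100 per arm, 200 in total). Then 202/(1 − 0.30) = 289, stated as 290.

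**Step 2: standard errors and intervals.** For a stratum with n per arm, SE = 5.3 × √(2/n). For a two-level interaction, SE = √(SE₁² + SE₂²). Half-width = 1.96 × SE.

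| Split | n per arm in each stratum | Stratum SEs (mg) | Interaction SE (mg) | Stratum half-widths (mg) | Interaction half-width (mg) | Interaction/stratum ratio |
|---|---|---|---|---|---|---|
| 50/50 | 50.5, 50.5 | 1.055, 1.055 | 1.492 | 2.07, 2.07 | 2.92 | 1.41, 1.41 |
| 70/30 | 70.7, 30.3 | 0.891, 1.362 | 1.627 | 1.75, 2.67 | 3.19 | 1.83, 1.20 |
| 80/20 | 80.8, 20.2 | 0.834, 1.668 | 1.865 | 1.63, 3.27 | 3.65 | 2.24, 1.12 |

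The ratio is √(1 + n₁/n₂), so with a common SD it depends only on the split.

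The centre is wrong as well as the width. Take a 50/50 split with estimates of exactly 2.1 mg in both strata. Each stratum's own interval is 2.1 ± 2.07, or 0.03 to 4.17 mg. The interaction estimate is 0, with interval −2.92 to 2.92 mg. Drawing the second around a point at 2.1 mg describes neither quantity.

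**Step 3: what comparing stratum significance would do.** Suppose the true effect is 2.1 mg in both strata, so there is no interaction. With stratum powers p₁ and p₂ (two-sided 5%, normal approximation), the chance that exactly one stratum is significant is p₁(1 − p₂) + p₂(1 − p₁).

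- 50/50: 0.512 × 0.488 + 0.512 × 0.488 = 0.50
- 70/30: 0.654 × 0.662 + 0.338 × 0.346 = 0.55
- 80/20: 0.712 × 0.758 + 0.242 × 0.288 = 0.61

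The interaction test is falsely positive in 5%.

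**Step 4: what the interaction test can detect.** Its power for a 2.1 mg difference in effect between strata is 29%, 25% and 20% at the three splits. It is the right test, but a weak one at this sample size.

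**Step 5: the App/session factor.** Section 2.1 gives the web-based support to the intervention arm and describes the comparator as usual care with a leaflet. The categories in section 5.3.4 depend on use of the intervention after randomisation. Unless controls can be placed in the same categories, every control falls outside the factor. Then neither a randomised within-stratum contrast nor a treatment-by-subgroup interaction can be estimated.

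**The case against.** The strongest reply is that the plan already contains the right test. Section 5.3.4 pre-specifies the interaction term, gives the stratified models the job of estimation, and nowhere says that strata will be compared by significance. Stratum estimates followed by an interaction test is a common layout. The plot sentence may be loose drafting for differences with their own intervals plus the interaction result.

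Most of this stands, and it rules out two stronger readings that a reader might infer. One is that the plan cannot show whether effects differ. It can, because the interaction model is specified. The other is that the SAP will judge effect modification by stratum p-values. It does not say so. The ordering creates that risk, and the 50% to 61% measures the risk, not a planned procedure.

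The figures also have limits. They use the unadjusted SD, whereas the primary model adjusts for baseline activity. The width ratios would be unchanged by a smaller common SD, but the discordance and power figures would move. At an equal split 2p(1 − p) cannot exceed 50%, so there the discordance would fall as stratum power rose above one half. It is also tempting to quote 1 − 0.95⁷ = 0.30 for at least one false positive in seven interaction tests. That assumes independence, yet the two BMI factors plainly overlap and the App/session factor may not be testable. Nor would ranking the interaction first reduce it. It is a reason for an exploratory label and no more.

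The reply does not rescue the plot sentence. Programmers work from the SAP text, and as worded it asks for the wrong interval. It also leaves unsaid which result supports a claim that effects differ.

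**Conclusion.** The concern holds on two counts. The analysis that answers the stated aim is ranked second and is not named as the basis for inference. The forest plot, as worded, attaches the interaction's interval to a treatment difference. For two-level factors split between 50/50 and 80/20, that interval is 1.12 to 2.24 times as wide as the correct one and is centred on a different quantity. For three-level factors no single such interval exists. If strata were compared by significance, a spurious contrast would appear in about 50% to 61% of trials with equal effects, against 5% for the interaction test.

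The width ratios rest on the assumed splits and a common SD. The discordance figures rest also on 202 evaluable participants, an unadjusted SD of 5.3 mg and a true effect of 2.1 mg in both strata. The App/session factor is a special case in which the planned interaction cannot be estimated unless controls can be classified.

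This should be corrected before analysis. It bears on how the subgroups are read, not on the primary result.

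**What to change.** Amend section 5.3.4 as follows.

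- Name the treatment-by-subgroup interaction test as the sole basis for any claim of effect modification, with a joint test for three-level factors.
- Plot each subgroup's treatment difference with its own 95% confidence interval, and give the interaction p-value in a separate column.
- Label all subgroup analyses exploratory, noting the low power for interaction.
- Leave the App/session factor out of the interaction analysis unless control participants can also be classified on it.

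A tie rule for women exactly at the median age would be a useful clarification. Changing the age cut itself is optional and not part of this point.

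The cost is SAP wording and plot code. No new data are needed and the primary analysis is unchanged.
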